To address the above gaps in knowledge, we designed and are close to finishing an original 2-year, randomized, controlled 1:1 RCT (continue vs discontinue), rater-blinded DMT discontinuation study (DISCOMS, NCT#: 03073603). The last of 260 patients was enrolled on February 4, 2020. Last patient, last visit will be in August 2021 (note, not all will be followed for two years, with shortest final follow-up at 18 months in a minority of late enrollees). While this is the first RCT of DMT discontinuation, others are underway in France (NCT03653273) and The Netherlands (NCT04260711). Among focus groups employed during the operation of DISCOMS, it was very clear that one of the main limitations of the study was relatively short duration of the follow-up. Herein we propose to address this limitation with a non-randomized, yet rater-blinded protocol to extend the follow-up of 100 participants from the original DISCOMS cohort by at least 12 months. In essence, the first 100 participants from the DISCOMS primary study who have already successfully completed the primary DISCOMS study (i.e. did not fail on the primary outcome of a new relapse or Brain MRI lesion), retained their original drug assignment (continue or discontinue) at the end of their participation in DISCOMS, and agree to participate in the extension will be included for a minimum of 12 more months of follow-up as assessed at a single visit. This is a pragmatic clinical trial, based on real world patterns of patient decision-making. As such, study visits will be attached to routine office visits when possible, and the patient/their insurance will be responsible for payment of standard of care aspects related to the study. This will include drug costs, the annual brain MRI scans at year one, and all routine safety monitoring as would be obtained in a typical office setting for that individual medication. The funding agency, EMD Serono (a biopharmaceutical business of Merck Pharmaceuticals KGaA), will be responsible financially for all research aspects, including data acquisition, all research personnel, and all regulatory review. In addition, while this is a discontinuation trial, all patients will be aware of their medication assignment, while observers of the main outcomes (relapses, MRI changes and the EDSS) will be blinded.

III. Research Methods

A. Outcome Measure(s):

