All participants will undergo the T_1 visit, which will include a formal, blinded relapse assessment by the Examining Physician (EDSS rater) in conjunction with the PI (see section E). Prior to enrollment, the enrolling physician will certify, based on their personal review of the prior MRI scans and/or reports which will include data from the 24 month primary DISCOMS trial, that the scans have been stable for a minimum of 4.5 years (review of minimum of two scans, although it could be more, separated by at least 4.5 years). MRI scans at T_1 , 36+ months after onset of participation in the primary trial, will be performed as per usual SOC, paid for by patient insurance, at whatever site is normally used by the patient (preferably the same scanner each time, and preferably the same scanner as the investigation site), and should be done on a MRI machine with magnet 1.5 Tesla or greater, with and without contrast. Gadolinium may be withheld at the discretion of the PI or request of the patient. The window for T_1 MRIs will be 60 day before or 120 days after the T_1 study visit, and will be analyzed by a central, board-certified, blinded neuro-radiologist for new activity compared to prior scans. All MRI scans will be read locally for safety and clinical purposes, and PIs will communicate any significant MS or non-MS findings to the primary neurologist (should they not be the primary neurologist). Any new lesion documented on the T_1 MRI scan will prompt delivery of a notice within 48 hours, to the PI, that the patient has achieved the endpoint of the study, with a description of relevant findings.

In the event of a suspected relapse, the patient will be instructed to contact their physician and the study coordinator at their local site within 48 hours of new symptoms and come in for an unscheduled visit and relapse evaluation within seven days of symptom onset. Use of corticosteroids will be at the discretion of the patient and the local PI or other physician. Use of systemic steroids to treat MS symptoms will be concluded to be a Protocol-defined relapse. As at scheduled visits, the determination of a relapse at an unscheduled visit will be made by the blinded EDSS examiner, who will perform the EDSS and only then receive information about recent clinical history.

D. Risks/Safety:

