symptoms (defined as worsening of 0.5 point on the EDSS or worsening by 1.0 or more points on the pyramidal, cerebellar, brainstem or visual functional system scores); symptoms lasting at least 48 hours in the absence of fever; and preceded by stability or improvement for at least 30 days. Any use of systemic steroids to treat MS symptoms will be counted as a Protocol defined relapse, regardless of when the patient was seen.

• Out of window relapse

Same as a protocol defined relapse, except that the patient was not seen within the 7-day window.

• Suspected relapse

Relapse that fails to meet the above situations, but may have been a relapse –i.e. all circumstances point to a relapse, but upon examination by the examining physician, no residual or change in the EDSS is noted.

Not a Relapse

Pseudo-relapse, i.e. a worsening of pre-existing neurological symptoms in the context of any significant stressor, including, but not limited to, infection, or physical, psychological or mental stress, as determined by the treating physician; or other symptoms felt not to be related to MS.

For the primary outcome, we will use Protocol defined relapse for analysis, with secondary analyses combining this with Out of window and Suspected relapses. For the above categorization, it is imperative that the subject be seen at time of relapse. Once the patient feels that they have experienced a relapse, the patient needs to contact the PI and study coordinator as soon as possible. Patients need to be seen at the clinic ideally within 1-3 days, and within 7 days at the latest, of onset of symptoms or the relapse will not qualify as a Protocol defined relapse. If the patient is unable to identify whether he/she is experiencing a relapse and does not contact the clinic to be seen within 7 days, it does not qualify as a Protocol defined relapse. When subjects are not scheduled for a clinic visit, the coordinators will call them once at the 30 month time period to assess potential relapses. The purpose of this phone call is to determine whether the patient is experiencing a relapse, or has experienced a relapse since the last clinic visit or phone call. As with scheduled visits, at an unscheduled visit the Examining Clinician will determine if a relapse occurred based on the EDSS evaluation, and a post-EDSS review of the presenting symptoms.

Or

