2. New Brain MRI lesion. This will be defined as any new or clearly enlarging T2 lesion at least 3 mm in size felt to be due to MS, regardless of whether it is associated with enhancement after the injection of Gadolinium. Development of new or more overt T1 hypointensities not associated with a new or enlarging T2 lesion will not be considered a new lesion.

A participant will be determined to have achieved the primary endpoint if they have either a new Protocol defined relapse or a new/enlarging brain MRI lesion. If any study participant achieves an endpoint, they will be referred back to their primary neurologist for consideration of restarting a MS DMT of their choice, or switching to an alternative DMT (if they were in the continuation arm). They will continue to be followed at all study time points with all procedures. This is a pragmatic trial, so individuals will continue to receive care from their primary neurologist (in many cases, this will be the Treating physician/PI as well). At all times, it will remain the choice of the patient and their physician to maintain or change the MS DMT. Any worsened neurological symptoms attributed to MS that are treated with systemic steroids, regardless of characterization above, will be counted as a Protocol defined relapse. In this context, it is imperative that patients contact the local PI of the study first and foremost, so that decisions about the use of steroids may be made by study personnel, and steroids used or not used after the determination of relapse status per the protocol.

An adverse event (AE) is the appearance or worsening of any undesirable sign, symptom, or condition occurring after starting the study even if the event is not considered to be related to study conditions or assignment. Study conditions or assignment includes assignment to continue or discontinue prior DMT. Medical conditions and diseases present before starting the study are only considered AEs if they worsen after starting the study. Abnormal laboratory values or test results constitute AEs only if they induce clinical signs or symptoms, are considered clinically significant, or require therapy.

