Blinding of outcome measures is very important. As this is a pragmatic study in which the research component is added on to the basic clinical visit, the Treating Physician/PI will have obtained a relapse history as part of that routine visit, yet is not blinded to the patient's medication assignment. The definition of relapse includes performance of the EDSS, and the separate EDSS Examining Clinician will be blinded to medication assignment, as well as to the relapse history, when doing the EDSS. While it might be preferential to have a relapse assessor separate from both the PI and the EDSS rater, this is impractical due to costs, the requirement to have a third clinician available at the visit, and the extra time of the visit. Thus, we will ask the PI to do a relapse assessment based on symptoms, but only make this information available to the EDSS Examining Clinician AFTER the EDSS is completed. The EDSS Examining Clinician will make the final assessment as to whether a Protocol defined relapse has occurred. While MRI readers and Examining Clinicians will be blinded to the patient's medication assignment, patients will not be blinded to medication assignment. Thus interpretation of the secondary Aims and Hypotheses as they relate to PROs will be potentially confounded by patient bias.

It is possible a patient may have asymptomatic changes on a surveillance spine MRI scan, which is not part of the protocol or SOC. Most new spine lesions will have clinical symptoms and signs associated with them, however, limiting the significance of this issue.

This protocol, if taken as an independent study of participants who have been randomized and followed on treatment or off treatment for two years for an additional follow-up period will not have sufficient power to answer the question of non-inferiority during this extension period. If taken as a continuation of the original protocol, it then operates under the power considerations designed in the original protocol (NCT03073603). We acknowledge the insufficient power of this extension study to address non-inferiority, but still expect to obtain valuable information. Through this extension, we will be able to track rates of relapse or MRI scan changes and collect information on effects of withdrawal from therapy, disease progression, and quality of life of these older MS participants over a longer follow-up period.

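### Steroid treatment chosen by unblinded people counts automatically as a primary-outcome relapse, yet the protocol calls relapse blinded and the examiner's call final; reconcile the text and add one sensitivity run.

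*Combined protocol and SAP*

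**What the plan says.** The steroid rule appears three times in the protocol.

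- Section III.C, on suspected relapses: "Use of systemic steroids to treat MS symptoms will be concluded to be a Protocol-defined relapse".
- Section III.D, inside the definition of the Protocol defined category: "Any use of systemic steroids to treat MS symptoms will be counted as a Protocol defined relapse, regardless of when the patient was seen".
- Section III.D, after the MRI endpoint: worsening attributed to MS and "treated with systemic steroids, regardless of characterization above, will be counted as a Protocol defined relapse".

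Section III.C also says who decides: "Use of corticosteroids will be at the discretion of the patient and the local PI or other physician". Section II states that "all patients will be aware of their medication assignment". Section III.E says that the Treating Physician/PI "will have obtained a relapse history as part of that routine visit, yet is not blinded to" the assignment.

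The blinding statements point the other way. Section II contrasts the patients' knowledge with the assessors' position, "while observers of the main outcomes (relapses, MRI changes and the EDSS) will be blinded". Section III.E says: "The EDSS Examining Clinician will make the final assessment as to whether a Protocol defined relapse has occurred". Sections III.C and III.D give the blinded examiner the determination at unscheduled visits, and the category definition in III.D calls for an EDSS change that the examiner observes blind.

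Protocol defined relapse is the relapse component of the primary outcome (III.D; III.F, Aim 1). The only planned variation, in III.D, widens the definition by adding Out of window and Suspected relapses.

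**The concern.** Under the steroid rule, an episode that the blinded examiner would class as Suspected, Out of window or Not a Relapse becomes a primary event once steroids are given for symptoms attributed to MS. Two of the parties to that decision, the patient and the local PI, know the arm. Whether the third, the other physician, is blinded is not stated.

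If knowing the assignment shifts the threshold for treating symptoms, event counts can differ between arms without any difference in disease. Section III.E acknowledges bias from unblinded patients only for the patient-reported outcomes, so the plan does not recognise this path into the primary outcome. With few events expected (III.F, Aim 1), a small number of such episodes could matter, and no planned analysis would show it.

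**Working it through.** **1. The passages side by side**

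| Question | Steroid rule (III.C, III.D) | Blinding statements (II, III.C, III.D, III.E) |
|---|---|---|
| What makes the event? | Steroid treatment of MS symptoms | Examination change seen by the blinded examiner |
| Does the 7-day window apply? | No | Yes |
| Who controls it? | Patient, local PI or other physician | Blinded EDSS examiner |
| Can the other route override it? | No; counts whatever the category | Examiner's assessment is final; no exception stated |

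Section III.D asks patients to contact the local PI first, so that steroid decisions follow the relapse determination. This improves the order of events but does not close the route: that PI is unblinded, and the episode still counts whatever the examiner decided.

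**2. The plan's own figure**

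Inputs (III.F, Sample Size): 50 per arm, 10 discontinue failures and 3 continue failures. One-sided Fisher exact test:

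p = Σ(k ≥ 10) C(50,k)·C(50,13−k) / C(100,13) = 0.0357, which agrees with the stated 0.036.

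**3. One event in that example**

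The documents give no rate of steroid-only events, so these are illustrations. One event at 50 per arm is 1/50 = 2.0 points. With the 59% discontinue share projected in III.C it is 1/59 = 1.7 or 1/41 = 2.4 points.

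| Discontinue vs continue (50 each) | One-sided p |
|---|---|
| 10 vs 3 (plan) | 0.036 |
| 9 vs 3 (one of the ten was steroid-only) | 0.061 |
| 8 vs 3 (two were steroid-only) | 0.100 |
| 11 vs 3 (one added in the discontinue arm) | 0.020 |
| 10 vs 4 (one added in the continue arm) | 0.074 |

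**4. One event against the 0.08 margin**

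The criterion (III.F, Aim 1) is a 95% upper bound below 0.08. Wald upper bound: d + 1.96·√[p₁(1−p₁)/n₁ + p₂(1−p₂)/n₂].

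- 1/50 vs 1/50: 0 + 1.96·√(0.000392 + 0.000392) = 0.055, criterion met.
- 2/50 vs 1/50: 0.02 + 1.96·√(0.000768 + 0.000392) = 0.087, not met.
- 3/50 vs 3/50: 0 + 1.96·√(0.001128 + 0.001128) = 0.093, not met even with equal arms.

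The crossing point depends on the split. At 59 and 41, 2 vs 1 gives 0.076 (met), while 3 vs 3 gives 0.075 (met) and 4 vs 3 gives 0.097 (not met). The planned Kaplan-Meier analysis linked to the parent trial would give different bounds.

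**5. Direction**

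Readier treatment off therapy adds discontinue-arm events. That works against showing non-inferiority and towards a false signal of harm. Readier treatment in the continue arm does the reverse. Nothing in the documents settles which would occur.

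**The case against.** The best defence is that this is a stated exception, not an oversight. It is written three times, once inside the definition itself, and III.C puts it directly beside the sentence giving unscheduled determinations to the examiner. It also has a rationale: III.A wants a sensitive safety endpoint that catches mild activity, and section II notes that steroids can reduce the severity and duration of a relapse, so treatment might erase the change the examiner needs to see. This stands. It is why the rule can remain in the primary definition. It does not supply the exception missing from III.E, nor make the route blinded.

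Exposure may also be limited. The exclusion criteria in III.B bar steroid use for an actual or possible relapse during or since DISCOMS, which as written would close this route before extension entry. That criterion sits uneasily with the stated inclusion of relapses after DISCOMS, so how far it narrows the problem is unclear.

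Power is a further point. Section III.E concedes that the extension alone cannot settle non-inferiority, III.F makes estimation the main goal, and 3 vs 3 already misses the margin. Steroid-only events are therefore not the main obstacle to an extension-only non-inferiority result. That stands too.

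A reader might go further and infer that the rule biases the trial towards non-inferiority, so that such a claim should depend on confirmed events alone. The documents do not support this. Under the most obvious mechanism the extra events fall in the discontinue arm, and removing them makes non-inferiority easier to show. Such a condition would protect only against the opposite pattern.

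**Conclusion.** The inconsistency is real: the examiner's assessment cannot be final if steroid treatment overrides it, and the blinding described for relapse does not extend to events that qualify only through steroids. The MRI component, read centrally and blind, is unaffected.

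The size is unknown because the documents give no rate of such events. One event is about 2 points at 50 per arm, a quarter of the 0.08 margin, and in the illustrations a single event can move either conclusion. Those results assume 50 per arm, crude proportions with Wald bounds and, for the Fisher comparison, a one-sided 0.05 threshold that the plan does not state. They show sensitivity, not a forecast. The direction of bias is open, with a false signal of harm as plausible an exposure as false reassurance. It would also go too far to infer that the primary outcome as a whole is unblinded. The point merits a text correction and one added analysis.

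**What to change.** 1. **Reconcile the text.** Either III.E states the steroid exception and acknowledges, with section II, that this route into the primary outcome is not blinded, or III.C and III.D let the examiner's assessment stand. Keeping the rule in the primary definition is acceptable.
2. **Flag the events.** Identify events that qualify only through steroid use: examiner criteria not met, or not seen within the window. The CRF relapse category, concomitant medication records and SAE reports may suffice. If the rule overwrites the examiner's category, add one flag that preserves it. Report the number by arm.
3. **Prespecify one sensitivity run of Aim 1** counting only Protocol defined relapses confirmed by the blinded examiner and centrally read MRI lesions. Report any conclusion of harm or of non-inferiority alongside it. Neither conclusion need be conditional on this run.

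The cost is a short amendment, at most one CRF field and one extra analysis. The two runs may differ and would then need explaining. For the linked Kaplan-Meier version, steroid-only events in the parent trial must be identified in the same way; otherwise the sensitivity run should be restricted to the extension period. When or whether steroids are used does not change.

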This will be a non-randomized, rater-blinded pragmatic trial, which is an extension of the randomized discontinuation trial (RDT)⁸², DISCOMS. While RDTs have been done in cancer^{83,84} and rheumatoid arthritis patients,⁶⁶ the original DISCOMS protocol was the first such study in MS. For this protocol, a subset of 100 subjects of the original 260 enrolled will be followed. Study sites will be limited to the top 10 recruiting sites across the United States from the DISCOMS study due to financial and cost-effectiveness issues. Those sites will have participants who have completed 18-24 months of the primary study. In practice, the vast majority, if not all, will have completed 24 months. We will explicitly include any who have completed, including those who already have exceeded 12 additional months after completion of the primary trial. Individuals who have successfully completed (retained original drug assignment and did not meet the primary endpoint of DISCOMS) the primary DISCOMS trial and are willing to retain their original drug assignment after completion and for an additional 12 months will be offered entry into the extension. The only exception to that will be individuals who continued the original drug assignment during and after the primary trial, up to 24 months, but who then had a relapse, new MRI lesion, or other MS-related reason between months 24 and 36 which resulted in their change of medication assignment. These individuals can and should be included, and counted as "failing" during the extension trial completing the Kaplan-Meier event free survival curve critical to the original hypothesis. A total of up to 100 patients will be consented and enter the extension trial, regardless of assignment, on a first come first serve basis to avoid selection biases to the extent possible. The intent is to take the first 100 who fulfill criteria and agree to participate. The plan is for a 50/50 distribution, but there may not be exactly 50 in each group. As of December 15, 2020, 123 had completed participation of the primary 24-month study, and information as to DMT use plans after finishing 2-years participation in DISCOMS was available for 84/123, 42 in each group (see Table 1 below). Notably, in the Discontinue group, 86% remained off DMT while only 60% in the Continue group plan to remain on a DMT (23/42 on the same DMT, two switching to an alternative). Overall 73% remained in the primary assignment grouping. If these ratios stay consistent as more finish DISCOMS, discontinuers will account for roughly 59% of the total enrolled in the extension trial. Also, of the 123 completers, 49 have also gone at least an additional 12 months since completion of DISCOMS, and they will be offered entry into the extension trial, should they otherwise fulfill criteria. There will be no placebo and no sham treatment. (Please see the statistics section the extension ns for power analyses discussions).

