The occurrence of AEs should be sought by nondirective questioning of the patient at each visit during the study. Adverse events also may be detected when they are volunteered by the patient during or between visits or through physical examination, laboratory test, or other assessments. All AEs must be recorded in the AEs eCRF with the following information:

1. the severity grade (mild, moderate, or severe)

- 2. its relationship to the study drug(s) (suspected/not suspected)
- 3. its duration (start and end dates or if continuing at final examination)

4. whether it constitutes a serious AE (SAE)

Serious adverse events such as hospital admissions for > 24 hours, new significant medical diagnoses such as cancer (other than basal cell carcinoma), and MS relapse requiring corticosteroid use will be ascertained at each visit. SAEs should be reported to the sponsor and entered into the electronic database within 24 hours of the event being reported to the study team. We will collect ongoing side effects of all DMTs, and non-serious adverse events in both groups, and report descriptive statistics and proportions on all adverse events. We will provide confidence intervals for the proportions and test them between treatments groups using the same type of methods used for the primary outcome.

E. Potential Scientific Problems:

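### The adverse event form asks about relation to study drug, not to continuing or stopping, and the planned between-arm AE test mixes steroid-treated relapses (already primary events) with other harms

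*Combined protocol and SAP*

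**What the plan says.** All references are to the combined protocol and SAP.

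- **AE definition (III.D Risks/Safety).** An event counts as an AE "even if the event is not considered to be related to study conditions or assignment". The next sentence explains the term: "Study conditions or assignment includes assignment to continue or discontinue prior DMT".
- **AE form (III.D).** Four items are recorded per event: severity, causality, duration and seriousness. The causality item reads "its relationship to the study drug(s) (suspected/not suspected". The protocol does not define study drug.
- **What discontinuers receive (III.C).** "There will be no placebo and no sham treatment". A participant in the discontinue group therefore takes nothing that could be called a study drug unless a DMT is restarted. The end of III.F says that AEs and SAEs in discontinuers who return to treatment are also monitored.
- **SAEs (III.D).** The examples are hospital admission, major new diagnoses and relapse: "MS relapse requiring corticosteroid use will be ascertained at each visit".
- **Relapse definition (III.D).** "Any use of systemic steroids to treat MS symptoms will be counted as a Protocol defined relapse", whenever the patient was seen. A Protocol defined relapse is one of the two components of the primary endpoint.
- **AE analysis (III.D).** Proportions are reported for all AEs with confidence intervals. The plan is then to "test them between treatments groups using the same type of methods used for the primary outcome". Nothing is said about setting relapses or MRI endpoint events apart.

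**The concern.** The trial asks what happens when older, stable patients stop treatment. Section III.D itself names recurrence of disease activity, and rebound after natalizumab, as possible harms of stopping. Section III.E lists effects of withdrawal from therapy among the information to be gained. A causality item tied to a drug does not fit that exposure. A site that takes it literally will answer *not suspected* for an off-drug participant whose event the investigator attributes to stopping. A site that takes it loosely will answer *suspected*. The field then means different things at different sites and in the two arms.

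The second issue is the content of the AE test. Steroid-treated relapses enter the AE and SAE proportions and are also primary events. A difference in SAEs could therefore be the primary result seen again, or a real difference in relapses could be offset by fewer drug side effects after stopping. Section III.G promises patients a view of risks against benefits. An unsplit AE total serves that purpose poorly.

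**Working it through.** **1. The plan's own figure.** The Sample Size paragraph of III.F supposes 50 per arm with 10 failures (20%) v 3 failures (6%) and gives a one-sided Fisher exact p-value of 0.036. Recomputing on 10/40 v 3/47 gives 0.0357 one-sided, so the figure is reproduced (two-sided 0.0713). The point does not depend on it. It is the source of the 20% and 6% used below, because III.D gives no AE rates.

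**2. The causality item against the AE definition.**

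| Situation at onset | AE definition: relation to assignment | Form: relation to study drug(s), literal reading |
|---|---|---|
| Continue arm, on DMT | can be judged | can be judged |
| Discontinue arm, off DMT | can be judged (assignment to discontinue is included) | nothing to judge against |
| Discontinue arm, DMT restarted | can be judged | can be judged, but only against the restarted drug |

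The mismatch is in the second row. The third row shows a further gap: none of the four listed items records whether a DMT was being taken at onset.

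**3. Where endpoint events enter the AE data.** A relapse requiring corticosteroids is a listed SAE. Systemic steroid use for MS symptoms makes the episode a Protocol defined relapse. The same episode is thus one event in two outcomes. Relapses not treated with steroids also fit the general AE definition. A new MRI lesion can qualify as an AE if considered clinically significant or if it requires therapy.

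**4. Size of the overlap (illustration).** Inputs:

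- p = 20% (discontinue) and 6% (continue), from the Sample Size paragraph.
- s = share of those failures that are steroid-treated relapses: assumed 25%, 50% or 100%. Failures also include MRI lesions, so 100% is an extreme.
- b = background SAE rate from all other causes: assumed 5%, 10% or 20%, equal in both arms and independent of relapse.

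P(any SAE) = 1 − (1 − b)(1 − s·p)

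Difference = (1 − b) · s · (0.20 − 0.06)

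| b | s = 25% | s = 50% | s = 100% |
|---|---|---|---|
| 5% | 9.75% v 6.425%: 3.325 points | 14.5% v 7.85%: 6.65 | 24.0% v 10.7%: 13.3 |
| 10% | 14.5% v 11.35%: 3.15 | 19.0% v 12.7%: 6.3 | 28.0% v 15.4%: 12.6 |
| 20% | 24.0% v 21.2%: 2.8 | 28.0% v 22.4%: 5.6 | 36.0% v 24.8%: 11.2 |

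The other harms are equal in every cell, so the whole difference comes from relapses. With relapses tabulated apart it is 0.

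**5. Offsetting in the other direction.** Take b = 10% in the continue arm. The discontinue background rate x that makes the two SAE proportions equal solves 1 − (1 − x)(1 − 0.20s) = 1 − 0.90(1 − 0.06s).

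- s = 25%: 1 − x = 0.8865/0.95, so x = 6.7%. A background rate 3.3 points lower hides the excess.
- s = 50%: 1 − x = 0.873/0.90, so x = 3.0%. A background rate 7 points lower hides it.
- s = 100%: x would be −5.7%, so full offsetting is impossible.

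**The case against.** The best case on the other side is that these are wording and reporting gaps with limited consequences. Much of it stands.

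- A reader might infer that the AE comparison cannot tell harm from stopping from harm of staying on a DMT. The documents do not support that. The planned comparison is of all AEs by arm and does not use the causality field. DMT side effects are collected. Each relapse is categorised on its own CRF, so relapses can be taken out at analysis.
- A reader might infer a table of related events that is one-sided by construction. No such table is planned.
- A reader might infer that suspected events in the discontinue arm are zero by definition. No coding rule says so, the term study drug is undefined, and discontinuers who restart a DMT can have suspected events.
- A reader might infer that the Medical Monitor would miss events caused by stopping. III.D gives the Monitor the safety data without a causality filter, and all SAEs are to be reported within 24 hours. What may be missing is the attribution, not the event.
- Relapses are not counted twice within one analysis. One event appears in two outcomes, and reporting it as an SAE is not itself at fault.
- The risk-benefit picture does not rest on the AE test, because Aims 1 to 3 report relapse, MRI, disability and patient-reported outcomes by arm.
- The rates s and b are assumed. The table shows that the overlap can matter, not how large it will be.

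Two things remain. The AE definition and the form disagree on what is being judged. And a safety test is announced with no statement that endpoint events will be shown apart, even though the data allow it.

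**Conclusion.** The point holds as a mismatch in one data item and a missing split in one analysis. Followed literally, the causality item gives no way to record a suspected relation to stopping for participants off DMT, which conflicts with the AE definition in the same section. The between-arm AE and SAE test includes steroid-treated relapses that are already primary events. Under the 20% v 6% example this alone produces about 3 to 13 points in the proportion with any SAE. That range depends on the assumed 25–100% steroid-treated share, the assumed 5–20% background rate, equal backgrounds in the two arms, and independence of relapse and other SAEs. The primary analysis, the sample-size example and the by-arm comparison of all AEs do not depend on the causality field. This is a cheap improvement to the safety reporting, not a flaw in the main result.

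**What to change.** 1. Reword item 2 of the AE form to *relationship to study assignment (continuing or having discontinued DMT): suspected / not suspected*, so that it matches the AE definition. Add one item recording any DMT being taken at onset. This also covers discontinuers who return to treatment.
2. Leave SAE reporting of relapses as it is. In the analysis, present the between-arm AE and SAE comparisons both with and without MS relapse and MRI endpoint events, and tabulate those events separately by arm.

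Cost: one wording change and one added item on the form, one extra table, and a short re-review of events already coded. The re-review is best done early, since attribution at onset becomes harder to reconstruct later.
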